Calls 7-10. All participants will get calls at Weeks 12, 20, 26 and 52 from research personnel who did not provide treatment to determine: smoking status (7-day point prevalence and daily calendar using timeline follow-back); use of alternative nicotine products (e.g., e-cigarettes); study medication use in the last 7 days; and withdrawal, self-efficacy, and adverse events (if using study medication). Calls 7, 9, and 10 will also assess the impact of Covid-19 on their life and their beliefs about Covid-19 and smoking. These assessment calls will not include counseling. If participants do not complete the 26 or 52-week assessment calls, we will send a brief assessment to them in the mail with a return envelope for them, and/or via text/email if the participant has consented to text/email communications, to report their smoking status. If participants report a serious adverse event or if they discontinue their study medication due to an adverse event, that information will be emailed to their primary care provider in the EHR by the Care Manager to enhance clinical care.

Table 1. Schedule of Cessation Screening Project Assessments and Interventions

| Assessments | | | Wk -1 | Day 2 | Wk 2 | Wk 4 | Wk 12 | Wk 20 | Wk 26 | Wk 52 |
|--------------------------------------|-----|----|-------|-------|------|------|-------|-------|----------------|----------------|
| | C1* | C2 | C3 | C4 | C5 | C6 | C7 | C8 | C9 | C10 |
| Eligibility screening | X | | | | | | | | | |
| Verbal consent and info sheet mailed | X | | | | | | | | | |
| Demographics | X | | | | | | | | | |
| Smoking history | | X | | | | | | | | |
| Covid-19 questions | | X | | | | | X | | X | X |
| Self-efficacy/ motivation | | X | X | X | X | X | X | X | X | X |
| Random assignment to treatment | X | | | | | | | | | |
| Tobacco dependence | | X | | | | | | | | |
| Health, alcohol use | | X | | | | | | | | |
| Withdrawal | X | X | X | X | X | X | X | X | X | X |
| Smoking status | X | X | X | X | X | X | X | X | X | X |
| Use of other tobacco products | X | X | X | X | X | X | X | X | X | X |
| Cannabis use | X | | | | X | X | | | X | |
| Medication use [†] | | | X | X | X | X | X | X | X | |
| Adverse events [†] | | | X | X | X | X | X | X | X | |
| Patient satisfaction | X | | | | | | X | | X | |
| Medication education and mailing | X | | | | | | | | | |
| Set target quit day ^{**} | | X | | | | | | | | |
| Intensive counseling (phone/video) | | | X | X | X | X | | | | |

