| Minimal counseling (phone/video) | | | X | X | | | | | | |
| Cotinine/anabasine | | | | | | | | | X ^a | X ^a |

*C1 will be conducted by the healthcare system Care Manager. All other calls will be conducted by research Health Counselors or other research staff

**The TQD will be set either 5 weeks from C2 to allow a week for medication to be delivered and 4 weeks for prequit medication use for those in the prequit medication condition, or 2 weeks from the C2 to allow a week for medication to be delivered and 1 week for prequit medication if the participant is in the

varenicline no-pre-quit medication condition

[†]Medication use and adverse events will be assessed for participants currently receiving study medication (this will vary by treatment condition)

[‡]All participants who report 7-day point-prevalence abstinence will be asked to provide a saliva sample to biochemically confirm abstinence.

Month 6 and 12 Biochemical Confirmation. Participants who report 7-day point-prevalence abstinence at the Month 6 and 12 follow-up call will be mailed a saliva collection kit with instructions on how to collect a saliva sample and mail it back to the Center. These saliva samples will be sent to a lab to assess the level of cotinine (a metabolite of nicotine and biomarker for smoking and other sources of nicotine). Please note, if participants have a detectable level of anabasine (a biomarker specific for combustible tobacco), we will also collect those results. Participants who report abstinence in the last 7 days at this visit but have a cotinine level >10ng/mL or who do not have provide a cotinine result will be considered to be smoking. When a participant demonstrates biochemically confirmed abstinence, that information will be conveyed to the primary care provider by the Care Manager via either email in the electronic health record or by changing the electronic health record smoking status.

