varenicline up to 35 days prior to the quit day is safe and effective. Participants assigned to the "OFF" level start their C-NRT use on their TQD or the standard Preparation varenicline, which starts 1-week pre-TQD (see Table 2).

Medication Duration: Extended vs. Standard. After Call 2, all participants will be mailed enough medication to get through the first month post-TQD and instructed to call a toll-free study number to have their refills mailed to them. Half of participants will be assigned to the Extended Duration (i.e., the "ON" condition); these participants will be able to use varenicline for 23 weeks post-TQD (24 weeks post-TQD if also randomized to preparation meds) or use C-NRT for 24 weeks post-TQD (see Table 2). The other half of participants will have varenicline for 11 weeks post-TQD (12 weeks post-TQD if also randomized to preparation meds) or C-NRT for 12 weeks post-TQD. We will urge all participants to use all of their study medication, regardless of whether they are abstinent or not.

Counseling: Intensive vs. Minimal. Half of the participants will be assigned to the Intensive Counseling condition and will receive four 15-20-minute counseling sessions occurring 1 week prequit, during the first week post-TQD and during Weeks 2 and 4 (see Table 1). During the first counseling call, the HC and participant will create a quit plan that the HC will then mail to the participant following the call. The counseling will be provided either via HIPAA-secure WebEx

Table 2. Medication Dosing

| | | Cessation Medication: Standard Duration (12 Weeks) | Cessation Medication: Extended Duration (24 Weeks) |
|-------------------------|------------------------|--|---|
| Varenicline | | 
No Preparation Meds:
 
 ▪ Days 1-3: 0.5 mg pill QD ▪ Days 4-7: 0.5 mg pill BID ▪ Day 8 (TQD)-Week 11: 1 mg pill BID 
Preparation Meds:
 
 ▪ Days 1-3: 0.5 mg pill QD ▪ Days 4-7: 0.5 mg pill BID ▪ Day 8-Week 16: 1 mg pill BID (TQD in Week 4) | 
No Preparation Meds:
 
 ▪ Days 1-3: 0.5 mg pill QD ▪ Days 4-7: 0.5 mg pill BID ▪ Day 8 (TQD)-Week 23: 1 mg pill BID 
Preparation Meds
 
 ▪ Days 1-3: 0.5 mg pill QD ▪ Days 4-7: 0.5 mg pill BID ▪ Day 8-Week 28: 1 mg pill BID (TQD in Week 4) |

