The question of primary interest is how treatments affect abstinence amongst diverse smokers amidst the variety of other factors that also influence smokers' ability to maintain abstinence, not whether such effects occur in a statistically adjusted sample. Therefore, the primary analyses will first be conducted without covariate adjustment, to ensure that covariate adjustment does not cloud interpretation or reduce external validity for various reasons. In secondary analyses, we will statistically control for covariates including: living with a smoker, biological sex, age, clinic, health system, use of other tobacco products at baseline, cigarettes per day at baseline,

and education. In addition, primary analyses will exclude participants who were switched to cNRT from varenicline or stopped using any medication during the FDA varenicline recall.

Self-reported point-prevalence abstinence at Weeks 12 and 26 and biochemically confirmed abstinence at Week 26 will be analyzed as secondary outcomes using methods similar to those used for the primary outcome. These analyses will allow us to examine the stability or robustness of the intervention component effects.

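### The Week 26 cotinine rule makes no provision for study NRT still in use, so it can bias confirmed abstinence against Extended C-NRT

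*Protocol*

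**What the plan says.** **The rule.** In the protocol, under Month 6 and 12 Biochemical Confirmation, people who report 7-day abstinence "will be mailed a saliva collection kit with instructions on how to collect a saliva sample and mail it back". "Participants who report abstinence in the last 7 days at this visit but have a cotinine level >10ng/mL" are counted as smokers, as are those with no result. The section gives no exception for NRT users, although it describes cotinine as "a metabolite of nicotine and biomarker for smoking and other sources of nicotine". It adds that "if participants have a detectable level of anabasine (a biomarker specific for combustible tobacco), we will also collect those results", but anabasine plays no part in the classification.

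**The drug schedule.** Under Medication Duration and in Table 2, Standard C-NRT ends 12 weeks and Extended C-NRT 24 weeks after the target quit date (TQD). Varenicline contains no nicotine. Under Interventions, Extended participants get one month of post-quit supply, then two more on request, then three more on request. Medication Duration adds: "We will urge all participants to use all of their study medication, regardless of whether they are abstinent or not".

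**What is recorded.** Under Calls 7-10, staff ask about "study medication use in the last 7 days". Table 1 marks medication use at Week 26 but not at Week 52, and its footnote limits the item to people currently receiving study medication.

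**The analysis.** The SAP (Implementation Challenges) dates the change from exhaled CO to cotinine to September 2023. It attaches the dated cut-offs only to the 12-month outcome. Under Primary Aim 1, "biochemically confirmed abstinence at Week 26 will be analyzed as secondary outcomes", next to self-reported abstinence at Weeks 12 and 26. Under Secondary Aims Analyses, 6-month confirmed abstinence is also an outcome for mediation, with medication use a candidate mediator.

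**The concern.** In someone who has stopped smoking but still uses the study patch or mini-lozenge, a raised cotinine shows the study drug and not relapse. Only C-NRT supplies study nicotine, and Standard C-NRT stops 14 weeks before the Week 26 call. Errors of this kind would therefore gather in the Extended C-NRT cells and not spread evenly over the design.

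That pattern pulls Extended below Standard, pulls C-NRT below varenicline, and shifts the Type x Duration interaction. In the mediation analysis, a participant could fail the outcome because of medication use, which would distort the link between that mediator and abstinence. What is at stake is a secondary outcome, meant to show how stable the component effects are, and the 6-month mediation results.

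**Working it through.** The plan gives no figure for this effect. Its nearest figures are the powers for 52-week abstinence, and they reproduce. With 304 per level, two-sided alpha .05 and a pooled two-proportion test, power is 0.871 for 15% v 25% (stated .87) and 0.814 for 20% v 30% (stated .81). They say nothing about misclassification at Week 26.

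**1. On-schedule use.** The end of Extended C-NRT is day 24 x 7 = 168 and the Week 26 call is day 26 x 7 = 182, a gap of 14 days. The mailed kit makes the sample later still. Assume, since the documents do not say, a starting cotinine of 100-500 ng/mL and a half-life of 12-48 hours. Time to reach 10 ng/mL is log2(start/10) x half-life:
- lowest: log2(10) x 12 h = 1.7 days
- highest: log2(50) x 48 h = 11.3 days

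All of this range is under 14 days, so on-schedule use gives no bias.

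**2. Room for late use.** The Extended supply is 1 + 2 + 3 = 6 months. At four weeks a month that is 168 days; in calendar months it is about 183 days, one day past the Week 26 call. Missed doses or late refill requests would extend use further. No arm is scheduled past Week 24, so use reported at Week 26 would be off-schedule. The documents give no frequency for it.

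**3. Share of Week 26 checks by cotinine (c).** Inputs from the SAP, Implementation Challenges: 432 at 6 months and 334 at 12 months by 7 December 2023; 538 recruited; 42 excluded, leaving 496.
- Monthly flow: (432 - 334)/6 = 16.3
- 1 September to 7 December, 3.2 months: 16.3 x 3.2 = about 52
- Later checks: 538 - 432 = 106, or 496 - 432 = 64 if the 432 already omits the 42
- c = (106 + 52)/538 = 29%, or (64 + 52)/496 = 23%

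This applies the September 2023 change to Week 26 and takes 1 September as its start. A later day in the month lowers c.

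**4. Size.** Let p be the proportion who are abstinent and return a sample, and f the share of those with study nicotine on board. The Extended C-NRT cell shifts by -p x f x c. Assume p = 20-30% and f = 10-50%.

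| Quantity | Low | High |
|---|---|---|
| Cell shift within the cotinine period (p x f) | 0.20 x 0.10 = 2.0 points | 0.30 x 0.50 = 15.0 points |
| Cell shift over all participants (x c) | 2.0 x 0.234 = 0.5 | 15.0 x 0.294 = 4.4 |
| Each main effect (half, equal cell weights) | 0.2 | 2.2 |
| Type x Duration difference in differences (full cell shift) | 0.5 | 4.4 |

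With p = 35%, the upper ends become 0.35 x 0.50 x 0.294 = 5.1 points for the cell and 2.6 for a main effect. These shifts are on the percentage-point scale; the planned model is logistic.

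**5. In people.** At 2:1 varenicline to C-NRT, with half of C-NRT Extended, the cotinine period holds 116/6 = 19 to 158/6 = 26 Extended C-NRT participants. Multiplying by p x f gives 19 x 0.02 = 0.4 to 26 x 0.15 = 3.9 participants. The 2:1 ratio also means C-NRT has a smaller share of late enrolments than of early ones. The value of c within C-NRT is then probably below 23-29%, and step 4 is on the high side in that respect.

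**The case against.** The strongest reply is that the plan schedules nobody to be on nicotine at Week 26. Extended C-NRT has tapered and stopped two weeks before, and the sample follows the call. That stands: without off-schedule use there is no bias.

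The sentence urging participants to use all their medication is about not stopping on account of smoking status. It is not an instruction to continue past Week 24. The question on recent medication use belongs to a set of items that the Calls 7-10 text applies to Week 52 as well, so it does not show that the investigators expect late use. It does show that late users could be identified.

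Other parts of the reply also stand. Most Week 26 checks used CO. Self-reported Week 26 abstinence is analysed alongside, and cotinine cannot alter it, so a divergence confined to Extended C-NRT would be visible. People who return no sample are already smokers under the rule, so only returned samples can be reclassified. The SAP sentence on moderators mentions 6- and 12-month abstinence without saying that it is confirmed, so the effect there is less clear than for mediation.

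A reader might infer that Week 26 results are biased as a matter of fact, or that a false Type x Duration interaction would steer the choice of packages. The documents support neither. The frequency of late use is unknown. The protocol and the SAP (Primary Aim 2) choose packages on 12-month abstinence and cost, and by then study nicotine ended 28 weeks earlier.

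What the reply does not remove is a rule that can give a wrong classification tied to factor level, while a marker specific to combustible tobacco is collected and left unused.

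**Conclusion.** The point holds as a conditional one. If some Extended C-NRT participants still use study NRT around Week 26, the cotinine rule can count abstainers among them as smokers, and the error runs against Extended Duration and against C-NRT.

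The likely size is small: about 0.5-4.4 points in the Extended C-NRT cell and 0.2-2.2 points in each main effect, or from under one to about four people. The SAP reports differences of 0.0-4.9 points for three of the factors. The main-effect shift is the right comparison with those, and its upper end is not negligible beside them.

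The figures rest on assumed abstinence and late-use rates, equal cell weights, and a cotinine share rebuilt from the SAP counts. The 12-month primary outcome and the optimisation are not affected by this mechanism. The change is worth making because it is cheap and because the SAP needs a Week 26 verification definition in any case.

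**What to change.** In the SAP:

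1. State the Week 26 confirmed-abstinence definition, with the CO and cotinine cut-offs and the dates each applies.
2. For participants verified by cotinine who report 7-day abstinence and study NRT use in the last 7 days, do not class as smoking on cotinine above 10 ng/mL alone. Use anabasine: detectable at the laboratory's stated limit means smoking. No returned sample still means smoking.
3. Say how a blank anabasine field is read, since the protocol speaks of collecting results only when anabasine is detectable. Confirm with the laboratory whether a blank means tested and not detected. Where anabasine was not run, keep the cotinine rule.
4. Report the cotinine-only version beside the new one, and use both in the 6-month confirmed-abstinence mediation analysis.
5. Limit the provision to study NRT. Nicotine from e-cigarettes or other sources can occur in any arm and is a wider question about the outcome.

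In the protocol, reconcile the supply described in months with the 24-week course.

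The cost is SAP wording and one derived variable from items already planned. There are three limits. Anabasine could miss some smokers who also use NRT. Medication use may be missing for those who answer by mail, text or email. The 7-day window at the call ends before the mailed sample is taken.

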608 (304 in the ON and 304 in the OFF levels of each factor with no missing data because missing=smoking) and $\alpha=.05$, we are powered at .87 to detect a difference between 15% and 25% in 52-week biochemically confirmed abstinence; we also have sufficient power (.81) to detect a difference between 20% and 30% in 52-week biochemically confirmed abstinence. Treatment optimization will be based on the effect size estimates of the main and interactive effects on 12-month abstinence, rather than statistical significance, consistent with our prior research¹⁵.

Protection of Human Subjects

Human Subjects Involvement and Characteristics. All EHR-identified smokers in a clinic will receive an invitation (in their preferred modality: mail, MyChart messages from the EHR, text) to find out more about smoking treatment by calling a healthcare system Care Manager. In addition, Medical Assistants (MAs), using an EHR-guided prompt, will inform all smokers attending in-person or tele-health visits that they will be getting a call from their clinic’s Care Manager, using an opt-out approach. The Care Manager will call the smoker and assess their interest in quitting smoking. Smokers who are interested in quitting in the next 30 days will be offered a variety of cessation treatment options, including the opportunity to participate in this smoking cessation study.

Specific eligibility requirements for this project are: age >17 years; smoking >4 cigarettes/day for the previous 6 months; able to read, write, and speak English; not currently taking bupropion or varenicline; if currently using NRT, agreeing to use only study medication for the duration of the study; medically eligible to use study medications (e.g., no severe renal disease, no allergic reactions to tested agents); and, if the participant is a woman of childbearing potential, using an approved method of birth control during treatment.

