Primary Aim 2: To identify two optimized smoking cessation treatments: one for varenicline and one for C-NRT. Data on both the 12-month abstinence effect sizes and costs of the different intervention components and combinations of components will be examined and multiple criteria decision analysis will be used to determine how to use each medication so that it is highly effective and but low in cost.

Secondary Aims: To determine: 1) whether person factors (e.g., sex, dependence, psychiatric history) moderate response to different treatment strategies; and 2) which proximal effects of each treatment factor mediate its long-term benefits; and 3) the main and interactive effects of the cessation interventions on cost-effectiveness and the cost-effectiveness of the optimal combinations of components for each medication type.

Implementation Challenges: Pandemic and Varenicline

Study recruitment began in November 2020.

In June 2021 Pfizer found that some lots of varenicline contained elevated levels of a novel nitrosamine that exceeded the level thought to be safe by the FDA for traditional nitrosamines. Therefore, we briefly paused recruitment. When we resumed recruitment, all participants were randomized to the C-NRT level of the Medication Type factor until November 2021 when we received IRB approval to use FDA-approved generic varenicline. When we were able to procure FDA approved varenicline, we changed our randomization ratio on this factor to 2:1 varenicline to C-NRT. When FDA initiated the varenicline recall, there were 42 participants actively taking

varenicline; 26 participants opted to switch to C-NRT and 16 stopped all medication. These 42 participants will not be included in the main outcome analyses.

We experienced significant implementation challenges with collecting in-person breath samples for biochemical verification of abstinence. In September 2023 we transitioned from using exhaled CO to verify abstinence ($\text{CO} < 6\text{ppm}$) to using cotinine assays on mailed saliva samples to verify abstinence ($\text{cotinine} \leq 10\text{ng/mL}$).

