Due to delays in implementing the study, and subsequent costs, caused by the global COVID pandemic, we were not able to reach our target sample size of 608. Preliminary data analyses conducted with data collected through December 7, 2023 indicated that there was only one factor that appeared to have a strong main effect for 6-month ($n=432$) and 12-month abstinence ($n=334$). The difference in abstinence rates for the two levels of each of the other 3 factors ranged from 0.0 to 4.9 percentage points. Given the lack of financial resources and the limited signal for additional main effects, we opted to close study recruitment at 538 (88.5% of the sample).

Sample Description

Participants' demographic and baseline smoking characteristics will be summarized using the appropriate descriptive statistics. The 42 people who were assigned varenicline and then discontinued varenicline and were switched to NRT after the FDA recalled Pfizer's varenicline will not be included in the main outcome analyses. We will conduct descriptive analyses to examine the differences between those in the varenicline condition who completed the treatment vs. those who switched to NRT during the FDA recall.

Outcome Analyses

Primary Aim 1: Identifying Main and Interactive Effects on Abstinence. The primary outcome is biochemically confirmed, point-prevalence abstinence (PPA) at 12-months post-TQD (based on $\text{CO} < 6\text{ ppm}$ for those assessed prior to September 2023 or salivary cotinine $\leq 10\text{ng/mL}$ for those assessed from September 2023 onward). We will conduct logistic regression analyses with predictors corresponding to the four factors using effect coding. The logistic regression models will include main and all interactive effects. Main effects will reflect the degree to which participants in the "ON" condition of a factor have significantly higher 1-year point-prevalence abstinence, relative to participants in the "OFF" condition for each factor, averaged across the other factors. These analyses will allow us to identify optimized treatments based upon main effects and interactions as they provide effect sizes (standardized regression coefficients) for the various intervention components and their combinations. We will conduct sensitivity analyses that compute abstinence means for those with CO vs. cotinine bio-verification. Due to the small sample sizes we will not do inferential testing on these comparisons.

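### The primary endpoint pools CO-verified and cotinine-verified abstinence without a period term, while Medication Type allocation also changed over time; a period-adjusted sensitivity run should be pre-specified

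*Protocol*

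**What the plan says.** **Outcome.** The SAP (Outcome Analyses, Primary Aim 1) defines the primary outcome by assessment date: CO below 6 ppm "for those assessed prior to September 2023 or salivary cotinine" at or below 10 ng/mL from that month on. The protocol (Month 6 and 12 Biochemical Confirmation) describes only the saliva stage. Self-reported abstainers who "have a cotinine level >10ng/mL or who do not have provide a cotinine result will be considered to be smoking". The same section says that cotinine also reflects nicotine from sources other than smoking. It adds that "if participants have a detectable level of anabasine (a biomarker specific for combustible tobacco), we will also collect those results", but gives anabasine no place in the classification rule. The SAP does not mention anabasine. The Table 1 footnote limits sampling: "All participants who report 7-day point-prevalence abstinence will be asked to provide a saliva sample".

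**Model.** The primary logistic model holds the four effect-coded factors and all their interactions, unadjusted. The covariate list for the adjusted analysis has no period or assay term.

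**Planned check.** "We will conduct sensitivity analyses that compute abstinence means for those with CO vs. cotinine bio-verification". The SAP adds: "Due to the small sample sizes we will not do inferential testing on these comparisons".

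**Completeness.** The SAP (Implementation Challenges) reports: "We experienced significant implementation challenges with collecting in-person breath samples for biochemical verification of abstinence". The protocol's power section takes 304 per level "with no missing data because missing=smoking".

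**Allocation.** By the SAP, recruitment began in November 2020 with varenicline in use. After the June 2021 pause everyone was assigned C-NRT until November 2021. Allocation then became 2:1 in favour of varenicline, and no end date is given. The 42 excluded participants had all been assigned varenicline before the recall.

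**The concern.** The confirmed rate can differ between the two periods for reasons unrelated to treatment, and in opposite directions:

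- A non-smoker who uses e-cigarettes or leftover or non-study NRT can exceed 10 ng/mL cotinine. If CO does not respond to these products (an assumption; the documents do not say), this lowers the later-period rate only.
- Breath samples that were never collected count as smoking. This lowers the earlier-period rate.

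Such a shift biases a factor contrast only if period is associated with the factor. The SAP reports an allocation change only for Medication Type. The all-C-NRT phase and the 42 excluded varenicline assignees both belong to the CO period, so early varenicline participants are fewer. Randomisation is at Call 2, which falls two to five weeks before the target quit date. People due at Week 52 from September 2023 were therefore randomised from about August 2022, after 2:1 began. If 2:1 was still in force, the cotinine period is rich in varenicline.

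Abstinence means by assay would show a shift between periods. They would not show how much of it has entered the Medication Type estimate. The protocol's power section bases optimization on effect sizes rather than significance, and the SAP puts three of the four factors' interim differences at 0.0 to 4.9 points. A shift of one or two points is therefore not negligible.

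**Working it through.** **1. The plan's own power.** Two-sided α = .05, 304 per level, power = Φ[(Δ − 1.96·√(2p̄(1−p̄)/n)) / √((p₁(1−p₁)+p₂(1−p₂))/n)].
- 15% vs 25%: (.10 − 1.96 × .0324)/.0322 = 1.13, power .871 (stated .87).
- 20% vs 30%: (.10 − 1.96 × .0351)/.0349 = .89, power .814 (stated .81).

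Both reproduce. They assume one homogeneous endpoint.

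**2. Share of Week 52 outcomes in the cotinine period.** Analysed: 538 − 42 = 496, taking the 42 to be among the 538. Suppose n=334 counts everyone due by December 7, 2023.
- 334 excludes the 42: (496 − 334)/496 = 162/496 = 33%.
- 334 includes them: (496 − 292)/496 = 204/496 = 41%.
- Week 26, from n=432: 64/496 = 13% or 106/496 = 21%.

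On this reading the true share could be higher, since some of the 334 may already be cotinine-verified. If 334 counts only people with data, the share is lower. For example, at an assumed 80% of those due, 334/.80 = 418 were due, giving 78/496 = 16% or 120/496 = 24%.

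**3. Spurious Medication Type difference with no true effect.** Observed rate in an arm = p[(1−s)(1−m) + s(1−u)], where
- p = true abstinence, 25% (assumed);
- s = the arm's cotinine-period share;
- u = share of true abstainers using non-combusted nicotine, 10-25% (assumed; taken as equal by arm or higher under C-NRT);
- m = extra share of CO-period abstainers lost to uncollected samples (assumed).

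With 248 per arm (assumed) and 2:1 throughout the cotinine period, 162 late splits 108 + 54 (s = .435 vs .218) and 204 late splits 136 + 68 (s = .548 vs .274). At equal u the difference is p(s_V − s_C)(m − u).

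| Scenario | 162 late | 204 late |
|---|---|---|
| 2:1, u = 20% both, m = 0 | 22.8% vs 23.9%: −1.1 | 22.3% vs 23.6%: −1.4 |
| 2:1, u = 25% both, m = 0 | −1.4 | −1.7 |
| 2:1, u = 10% vs 15-25%, m = 0 | −0.3 to +0.3 | −0.3 to +0.3 |
| 2:1, u = 20% both, m = 10% / 20% / 30% | −0.5 / 0 / +0.5 | −0.7 / 0 / +0.7 |
| 2:1, u = 10% vs 25%, m = 30% | +1.9 | +2.4 |
| 1:1 restored, equal u | 0 | 0 |
| 1:1 restored, u = 10% vs 15-25% | +0.4 to +1.2 | +0.5 to +1.5 |

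Entries are points, varenicline minus C-NRT. If use were instead higher under varenicline (25% vs 10%, m = 0, 204 late, 2:1), the result would be .25 × [(1 − .548 × .25) − (1 − .274 × .10)] = −2.7.

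**4. Scale.** The standard error of the contrast is √(2 × .25 × .75/248) = 3.9 points. The design target is 10 points.

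**5. What an additive period term does.** At equal u it returns the odds ratio from .93-.94 (u = 20%) to 1.00. At u = 10% vs 15-25% it leaves 1.02-1.09, so it removes a shift common to both arms but not a differential one. Its cost for the Medication Type estimate is the variance inflation 1/(1−r²). With 292 CO-period and 204 cotinine-period participants, two-thirds of the latter on varenicline, and an assumed CO-period varenicline share of 35% to 60%, r runs from .312 to .068 and the inflation from 1.108 to 1.005.

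**6. The other three factors.** With no change of allocation, a common loss only dilutes the effect. At u = 20% and m = 0, a 10-point difference becomes 10(1 − .327 × .20) = 9.3 or 10(1 − .411 × .20) = 9.2 points. Power for 20% vs 30% at 248 per level goes from .731 to .692 or .682.

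**The case against.** The SAP discloses and dates the assay switch, gives both cut-offs and plans a check. It justifies the unadjusted primary model and gives a reason for not testing. Its wording does not exclude means by factor level within assay. The modelled bias is small, rests on assumed inputs and is zero in several scenarios. At Week 52, study C-NRT ended at least 52 − 24 = 28 weeks earlier, so the cotinine question concerns mainly e-cigarettes and other nicotine. All of this stands. It is why the written analysis should remain primary.

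Four stronger readings are tempting, and the documents do not support them:

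- **That early allocation was entirely C-NRT.** Varenicline was assigned before the recall; only the phase from the June 2021 pause to November 2021 was all C-NRT.
- **That at least a third of outcomes are certainly cotinine-verified.** This holds only on one reading of n=334.
- **That a period-by-Medication Type interaction would settle the matter.** The standard error of the log ratio of period-specific odds ratios is about .44-.52. The largest modelled cotinine-period odds ratio is 1.26 (log .23). The SAP's small-sample caution is fair here.
- **That the cotinine rule is an error which anabasine would correct.** The rule is explicit, and the protocol encourages stopping all tobacco products. An anabasine-based outcome is a different endpoint, cannot be applied to CO-period participants, and may not be computable if only detectable results were kept.

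A split at September 2023 also does not isolate the assay, because the periods differ in varenicline source and enrolment cohort.

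**Conclusion.** The concern holds as a gap in the sensitivity plan, not as evidence that the primary result is biased. Two assays in two calendar periods feed one endpoint, one factor's allocation changed over the same calendar time, and no planned model adjusts for period. The table's range of -1.7 to +2.4 points depends on 25% abstinence, equal arm sizes, the assumed nicotine use and its ordering by arm, the unstated duration of 2:1, the reading of n=334 and the completeness of CO collection. Neither sign nor size can be fixed from the documents. A reader might infer a known bias against varenicline. That is unsupported, because lost breath samples, or more non-combusted nicotine use under C-NRT, would cancel or reverse it. The check is worth adding because it is cheap and the optimization rests on point estimates.

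**What to change.** Keep the written classification rule and the unadjusted model as primary. Add to the SAP:

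1. A sensitivity re-run of the primary model at Weeks 52 and 26 with an additive term for verification period, defined by the date the assessment was due. Preferably also add a term for randomisation phase (pre-recall, all C-NRT, 2:1, and a further level if 2:1 ended), and leave the all-C-NRT phase out of the Medication Type contrast in that run.
2. A table by period and Medication Type: sample-return rates among self-reported abstainers, and confirmed abstinence over everyone randomised.
3. The dates on which 2:1 allocation began and ended, and what n=334 and n=432 count.

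Optional: period-specific odds ratios with confidence intervals, labelled descriptive; and, only if anabasine non-detects were recorded, a smoke-free abstinence outcome labelled as a different endpoint.

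Cost: SAP wording, one extra model run per time point and one table; no new data. The period term inflates the variance of the Medication Type effect by about 0.5-11% under the assumptions above, and leaving out a phase loses some further precision. The report should say that a period difference cannot be attributed to the assay alone.
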